## 6.6 Sample Size:

**6.6.1 Patients:** We aim to recruit 50 unique patients over an 18-month period to use the care pathway. The Ottawa Hospital admits over 500 patients with acute exacerbations

of COPD annually and approximately 30% of these patients are admitted to the respiratory inpatient service (150 patients). Given that COPD exacerbations are twice as common in the winter months (22), we feel our recruitment target of 50 patients is feasible between November 2017 and May 2019.

**6.6.2 Health Care Professionals (HCPs):** We aim to recruit approximately 26 HCPs, 2 groups of 13 participants, to discuss of their personal experiences with the COPD care Pathway after an evaluation of the pathway.

## 6.7 Outcomes

**6.7.1 Primary: The primary outcome is the feasibility of using this COPD care model in a hospital setting.** In this practical experiment, feasibility will be defined by recruitment of 50 patients (3-4 per month x 18 months) to the care pathway, with an 85% completion rate (care model completion). This will be calculated using the number of completed pathway documents divided by the total number of care pathways initiated at the time of admission. We will critically review each document for completion.

**6.7.2 Secondary:** There are four secondary outcomes for this study.

**6.7.2.1 Qualitative Implementation Metrics:** Implementation of the care pathway will be evaluated by HCPs (nursing staff and allied health professionals). Participants are asked to complete a questionnaire and participate in a focus group with other HCPs. During focus groups, common themes for barriers to implementation will be identified using a-priori selected questions. We will consider success of implementation if no significant barriers are identified through group consensus in the focus groups and if 80% of questionnaire responses in each category fall into the “agree” or “strongly agree” responses.

**6.7.2.2 Knowledge Translation Metrics:** We will measure success in knowledge translation with achievement of 80% adherence to basic COPD care guideline standards including use of appropriate antibiotics, systemic steroids, bronchodilators, venous thromboembolism prophylaxis, and advanced directives documentation. Adherence will be calculated from direct review of the care pathway documents after completion.

**6.7.2.3 Patient Reported 'Health Confidence':** Health confidence is a measure of the engagement of a patient in his or her own health (24). Greater health confidence is associated with improved outcomes, better experiences with care, and improved health resource utilization and cost (24,25). Health confidence will be measured using a four-item scaled survey: 1) I know enough about my health, 2) I can look after my health, 3) I can get the right help if I need it, and 4) I am involved in decisions about me. Participants answer each of the statements with the following scale: strongly agree, agree, not sure, or disagree. Patients who report 'strongly agree' for each of the above-mentioned statements are considered to have a higher level of health confidence than participants who report 'disagree'. These statements have demonstrated adequate psychometric properties and construct validity in preliminary testing (26). Formal permission for utilization of this tool in this study was obtained from the developer ([name], R-Outcomes Ltd., Bristol, UK). The health confidence survey will be administered at the start of the education session in hospital, and repeated at 3 months, during a follow-up visit in the Pulmonary Function Test laboratory of the Ottawa Hospital, General campus. We aim for 80% completion of the "Health Confidence Score" among patients using the care model.

**6.7.2.4 Patient Reported 'Quality of life':** Patients quality of life can be measured with the "Health Related Quality of Life Score", or 'howRu' tool which has been validated against other quality of life tools. This tool is a four-item scaled survey: 1) Pain or discomfort, 2) feeling low or worried, 3) Limited in what I can do, and 4) require help from others. Participants answer each of the statements with the following scale: none, a little, quite a lot, or extreme. Those who report 'none' for each of the above-mentioned statements are considered to have a better quality of life than those who respond 'extreme'. These statements have demonstrated adequate psychometric properties and construct validity in preliminary testing (26). Formal permission for utilization of this tool in this study was obtained from the developer ([name], R-Outcomes Ltd., Bristol, UK). This survey will be administered at the start of the education session in hospital, and repeated at 3 months, during a follow-up visit in the PFT laboratory. We aim for

80% completion of the “Quality of Life Score” among patients using the care model

**6.7.2.5 Health Service Metrics:** We will use the Ottawa Hospital Data Warehouse (TOHDW) to measure length of stay, cost per weighted case, 30-day readmission, mortality, intensive care unit admission, intensive care unit length of stay, and number of hospitalizations in the 2-year window prior to the current admission. TOHDW is a relational database that captures clinical and administrative data for unique hospital encounters.

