## 6.0 METHODS

**6.1 Design:** a prospective, mixed-methods, cohort study design at The Ottawa Hospital (TOH) to evaluate feasibility of this complex intervention.

**6.2 Study population and Inclusion Criteria:** We will include adult patients admitted to the 6NW (Respirology ward) of the General campus at TOH with a primary diagnosis of acute exacerbation of COPD (AECOPD). The diagnosis is based on the admitting physician's assessment of the patient in the emergency room.

We will also include approximately 26 health care workers (nurses, physicians, and allied health professionals) who care for patients on the 6NW of the General campus at TOH who have implemented and worked with the COPD care pathway during the study duration.

**6.3 Time Frame:** Implementation and feasibility data will be collected for 50 patients who are hospitalized for COPD over the course of two flu seasons (2017-2018 and 2018-2019), which corresponds to the peak season for COPD-related hospitalizations (22).

**6.4 Consent Process:** Patients eligible for the study will be approached by the study respiratory nurse educator (RT), who is already part of the patients circle of care. The RT will ensure the potential participant understands the study and what it would require of them (two questionnaires: one in hospital and one during a 3-month post-discharge visit). If the patient accepts, the RT will ask them to review the Informed Consent Form and sign if they agree to participate in the study.

A member of the study team will approach Healthcare professionals (HCPs) who work on the Respiratory ward (6NW) of TOH, General campus and have used the COPD care pathway to participate in the study. The member of the study team will explain the study and ask if they would

like to participate. If they agree to participate, they will be given a consent form. The consent form requests a consent to complete a questionnaire and participate in the focus group with other HCPs. If the HCP chooses to participate, the signed informed consent is placed in one box, while the completed questionnaire is placed in another. This is to conserve anonymity of the questionnaire responses. Once focus group times and location are set, an email will be sent out by a member of the study team to inform those who consented to participate of the focus group time and location.

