**6.5 Implementation of the Goal-Directed Care Pathway:** Patients enrolled in the study will receive standardized treatment using an initial physician order set followed by a clinical care pathway (Appendix B). The order set and care pathway will be physically added to the patient's chart for daily reference by the health care team.

The care pathway (see Appendix B) consists of orders to be executed by the nursing staff, attending physician, and allied health professionals (respiratory therapy, occupational therapy, and physiotherapy, where applicable) while the patient is hospitalized. None of the components of the pathway extend beyond standard care that would be provided at TOH.

To initiate the care pathway, the first nurse to admit the patient will complete a frailty assessment and document the patient's clinical frailty score (8). This validated frailty score is associated with a set of expected treatment goals and outcomes for the patient during hospitalization and will serve to guide the subsequent care for the patient.

Following the frailty assessment, the care pathway is divided into three phases: rescue, optimization, and safe transition. The interventions in each phase are tailored to the COPD patient based upon their frailty rating. Evidence-based pharmacologic treatments, consultations with allied health professionals, medical services (e.g. Palliative care), and multidisciplinary educational interventions (Appendix A) are ordered in each phase where appropriate. In the safe transition phase, follow up with primary care, and referrals to pulmonary rehabilitation and the COPD outreach program will be arranged where appropriate.

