- 3) **At Study Conclusion:** Data collection in this phase will be from TOHDW. We will collect all health service outcome data up to 6 months post-discharge from the TOHDW. This will include initial hospital length of stay, mortality, ICU admission, 30-day readmission, and cost per weighted case.

|                        | DURING HOSPITALIZATION  |   |  |   | 3 MONTHS POST-DISCHARGE   | STUDY CONCLUSION |
|------------------------|---|---|--|---|---|------------------|
| STANDARD CLINICAL CARE | ADMISSION   | COPD PATHWAY PHASE 1  | COPD PATHWAY PHASE 2   | COPD PATHWAY PHASE 3  | COPD PATHWAY PHASE 4  |                  |
|                        | 
 
- Admission w/ AECOPD from ER
 
- MD completes Physician Admission orders
 
- Pt moved to Respiratory ward (ENW)
 
- COPD Clinical Pathway initiated
 
 | 
 
- Frailty rating completed by nurse (RN)
 
- Pathway instructions followed
 
   | 
 
- Pathway instructions followed
 
- COPD Education session completed
 
  | 
 
- Pathway instructions followed
 
- Ensure completion of Pathway documentation
 
- 3 month follow-up scheduled*
 
 | 
 
- 3 months post-discharge follow-up in the Pulmonary Function Laboratory at the Ottawa Hospital, General campus*
 
  |                  |

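### The feasibility rule in Protocol 6.7.1 shows that started pathways were completed, not how far the model reached 6NW, and its monthly pace does not multiply to 50

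*Protocol*

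**What the plan says.** Objective (a) in Protocol section 3.0 is the feasibility of implementing the care model on a respiratory ward. Section 6.7.1 decides this with two criteria. The first is "recruitment of 50 patients (3-4 per month x 18 months) to the care pathway". The second is an 85% completion rate, defined as the "number of completed pathway documents divided by the total number of care pathways initiated at the time of admission".

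The other targets in 6.7 also start from pathway use. For guideline adherence (6.7.2.2): "Adherence will be calculated from direct review of the care pathway documents after completion". The 80% questionnaire targets (6.7.2.3 and 6.7.2.4) apply "among patients using the care model". The staff approached under 6.4 are those who "have used the COPD care pathway to participate in the study".

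On who is started, section 6.5 says: "Patients enrolled in the study will receive standardized treatment using an initial physician order set followed by a clinical care pathway". It also says: "To initiate the care pathway, the first nurse to admit the patient will complete a frailty assessment". Figure 1 in 6.9 lists "COPD Clinical Pathway initiated" at admission, in the row for standard clinical care. Consent is a separate approach by the study respiratory educator (6.4).

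Section 6.6.1 sets 50 unique patients over 18 months, between November 2017 and May 2019. It supports this with about 150 COPD admissions per year to the respiratory service. Section 6.3 describes the period as two flu seasons.

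**The concern.** An eligible 6NW patient who is never started on the pathway enters neither feasibility figure. The rule can therefore be met whatever share of the ward's AECOPD admissions was started, provided that 50 patients were recruited and most of their documents were finished. That answers whether a started pathway gets completed. It does not answer how far the model was taken up on the ward.

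The difference matters for what follows. Objective (c) uses the pilot to plan a larger study, and section 7.0 names a cluster randomized trial, for which reach is a planning input.

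Two wording problems sit in the same criterion. The monthly pace and the duration do not multiply to the target. It is also not settled whether the denominator of the completion rate covers enrolled patients only or every patient started on 6NW.

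**Working it through.** **Inputs.** Target 50, pace 3-4 per month, 18 months, 85% (6.7.1). 50 over 18 months, November 2017 to May 2019; over 500 admissions per year, about 30% of them to the respiratory service, that is 150; exacerbations twice as common in winter (6.6.1). Two flu seasons (6.3). Assumptions: respiratory-service admissions approximate 6NW, and winter lasts 4 to 7 months from November.

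**Step 1: reproduce the target.**
- 3 × 18 = 54 and 4 × 18 = 72. The stated product is 54-72, so 50 is not reproduced.
- 50 / 18 = 2.8 per month.
- At the stated pace, 50 patients take 50/4 = 12.5 to 50/3 = 16.7 months, which is shorter than the stated 18.

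**Step 2: the completion criterion.** 0.85 × 50 = 42.5. With 50 pathways initiated, 43 must be complete (43/50 = 86%; 42/50 = 84% fails).

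**Step 3: 50 recruits against 18 months of admissions.**
- Flat rate: 150 × 1.5 = 225; 50/225 = 22.2%.
- Seasonal, with w winter months at double weight: base monthly rate r = 150/(12 + w). Over 18 months from November, w = 4, 5, 6, 7 gives 243.8, 247.1, 250.0 and 244.7 admissions; 50/N = 20.0-20.5%.

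**Step 4: two flu seasons only.** Admissions = 2 seasons × w months × 2r = 4wr.

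| w | r | Admissions | 50/N |
|---|---|---|---|
| 4 | 9.375 | 150.0 | 33.3% |
| 5 | 8.824 | 176.5 | 28.3% |
| 6 | 8.333 | 200.0 | 25.0% |
| 7 | 7.895 | 221.1 | 22.6% |

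**Step 5: is there a denominator elsewhere in 6.7?** Adherence is read from pathway documents. The patient questionnaires concern pathway users. The health service metrics in 6.7.2.5 are patient outcomes such as length of stay and readmission. The focus groups give themes and no proportion. The 150 per year in 6.6.1 supports the recruitment target and is not the denominator of any outcome.

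**The case against.** The strongest reply is that 6.7.1 states plainly what it measures and does not call it reach. Count targets are common in pilots, and 6.6.1 gives the pool, so a reader can place 50 against it. Section 6.8.1 refers some feasibility data to case report forms that are not shown and may hold a screening count. Staff focus groups ask about barriers to implementation, and section 7.0 adds monthly groups with physician trainees; either can bring out reasons why pathways were not started. All of this stands. It does not change the rule, which the protocol itself fixes and which uses no such count, and themes do not give a proportion.

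Four stronger readings are tempting and are not supported.
- **That the model would reach only a fifth to a third of the ward.** Fifty is a sample size. Refusals, repeat admissions, early completion of recruitment or pathways started outside the study could account for the rest.
- **That the true fraction could be far higher, up to nearly all patients.** Repeat admissions, or a 6NW share below the whole service, would raise it, but the documents give no figure for either.
- **That 50 to 53 recruits would fail.** Fifty is the target in 6.3, 6.6.1 and 6.7.1, and the bracket reads as a pace; 2.8 rounds to 3.
- **That initiated over admissions is automatically uptake.** If only enrolled patients are started, the ratio is capped by the target of 50 and by consent, whatever the ward could do.

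The doubt about the denominator is partly answered too. Section 6.5 names enrolled patients, and the standard-care row of Figure 1 fits its statement that nothing in the pathway goes beyond standard care. A clarifying sentence would settle it.

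**Conclusion.** The point holds in a limited form. Meeting the rule in 6.7.1 supports the statement that pathways which were started were completed. It does not show how far the model reached AECOPD admissions on 6NW, and no other quantitative outcome in 6.7 does. Planned recruitment is about 20-22% of 18-month admissions, or about 23-33% of admissions in two flu seasons. These figures rest on 150 admissions per year holding throughout, on the respiratory service approximating 6NW, and on a winter of 4 to 7 months. They show that the rule leaves reach open; they do not estimate it.

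The mismatch between 54-72 and 50 is a real but minor inconsistency in the success criterion. Both matters deserve correction, and neither undermines the design.

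**What to change.** 1. Keep the target of 50, restate the pace as about 3 per month (2.8), and state one recruitment window that reconciles the two flu seasons of 6.3 with November 2017 to May 2019 in 6.6.1.
2. State in 6.7.1 whether initiated pathways are those of enrolled patients only or of all patients started on 6NW.
3. Take the aggregate count of AECOPD admissions to 6NW in that window from the Data Warehouse and report it beside the numbers initiated and completed. If only enrolled patients are started, label the ratio a recruitment fraction, not uptake.
4. If this is not done, limit the feasibility conclusion to completion among patients started on the pathway.

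No uptake threshold is required. The cost is one aggregate count from a source already in use, plus wording; item 4 needs wording only. The downsides are that the result may look less favourable, that an administrative count only approximates eligibility (which rests on the admitting physician's assessment), and that counting non-enrolled patients' pathways may need ethics approval.

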## 6.8 Data Sources:

- 6.8.1 **Electronic Health Record, COPD Pathway Documents:** We will collect patient-related data using and some feasibility data using a combination of vOacis and the COPD care model document. These data points are detailed in the case report forms.
- 6.8.2 **Focus Groups and Questionnaires:** We will gather data from focus groups of HCPs to assess our implementation outcomes, and questionnaires provided to the HCPs who use the care models.
- 6.8.3 **Patient Questionnaires:** We will gather data from the COPD Assessment Test (CAT) and Health Confidence scores (HCS) to assess the symptom burden and engagement of patients.
- 6.8.4 **TOH Data Warehouse (TOHDW):** Health service metrics including length of stay, cost per weighted case, readmissions, mortality, and ICU admissions will be ascertained from the Data Warehouse. A separate Data Specification Form (DSF) has been initiated for this data request.

**6.9 Data Collection:** The following figure illustrates when data will be collected for participant during the study. The two focus groups will be conducted during the pilot in March 2018 with HCPs (nurses, physiotherapists, occupational therapists, and dieticians) who have used the pathway. Questionnaires of HCPs will be gathered prior focus groups.

Patient data will be collected at three time-points:

- 1) **During hospitalization:** Includes COPD Pathway Phases 1 to 3. Patient data relating to demographics, frailty rating, COPD diagnosis, lung function, oxygen use, smoking status,

and symptom burden will be collected from the hospital chart. The study respiratory therapist will enter this data in a Case Report Form for Respiratory Therapists. Patient participants are asked to complete a baseline health confidence and quality of life questionnaire at the beginning of hospitalization (Part A – Patient In-Hospital Questionnaire).

- 2) **3-Months Post-Discharge:** Includes COPD Pathway Phase 4. During a post-discharge visit in the PFT laboratory of the General Campus at TOH, patient participants will be asked to complete a follow up questionnaire (Part B – Patient Post-Discharge Questionnaire). During this visit, a review will be undertaken of community services accessed by the patients, and any referral issues will be rectified if needed.

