|   |         | Terminally Ill: 
 
Approaching the end of life.
 
Applies to people with a life expectancy less than 6 months, who are not otherwise evidently frail
 
   | 
 
Strongly consider palliative care consultation
 
Arrange hospice, long term care, or palliative care at home
 
  |  Social Work
 Palliative Care (MD to complete)

If returning home:
 OT  PT for services                               |                   |          |

CP 110 A (06/2017)

CHART

© THE OTTAWA HOSPITAL

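### Mortality up to 6 months after discharge comes only from a hospital-encounter database, so deaths at home, in hospice or in long-term care have no stated route into the data

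*Protocol*

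**What the plan says.** Section 6.7.2.5 lists mortality and 30-day readmission among the health service metrics to be measured from TOHDW, and describes the source: "TOHDW is a relational database that captures clinical and administrative data for unique hospital encounters". Section 6.8.4 repeats the assignment: "Health service metrics including length of stay, cost per weighted case, readmissions, mortality, and ICU admissions will be ascertained from the Data Warehouse". It adds that a separate Data Specification Form has been initiated for the request; that form is not part of the document.

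Section 6.9, third time point, sets the window: "We will collect all health service outcome data up to 6 months post-discharge from the TOHDW". The list that follows reads: "This will include initial hospital length of stay, mortality, ICU admission, 30-day readmission, and cost per weighted case". Mortality carries neither a time limit nor a place of death. Readmission is a 30-day outcome in 6.7.2.5, 6.9 and Figure 1; only 6.8.4 uses the word without a window.

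In the Clinical Frailty Scale table of Appendix B, the terminally ill row is defined as: "Applies to people with a life expectancy less than 6 months, who are not otherwise evidently frail". One of its expected goals of care is: "Arrange hospice, long term care, or palliative care at home".

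The only post-discharge study contact is the 3-month visit to the pulmonary function laboratory. It holds the follow-up questionnaire and a service check: "During this visit, a review will be undertaken of community services accessed by the patients, and any referral issues will be rectified if needed". Recording of vital status, or of why a patient did not attend, is not mentioned.

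**The concern.** The source and the window do not fit each other as described. An encounter database sees a death that occurs during an encounter. A patient who goes home or to hospice and dies there need not generate another encounter. Such a patient then looks the same in the data as one who is alive and well.

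The gap is not spread evenly. The terminally ill row is defined by a life expectancy shorter than 6 months, the same length as the follow-up window, and it is the row whose goals of care point to settings outside the hospital. Any loss would therefore be concentrated among patients likely to die within the window.

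What is at stake is modest but real. Objective (c) in section 3.0 uses this pilot to plan a larger study of health system and patient-reported outcomes, and the Project Summary says the study will assess the team's ability to measure health service outcomes. An incomplete mortality figure would be a poor planning input. It would also leave unanswered whether post-discharge death can be ascertained at all.

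**Working it through.** **Stated figure.** The protocol gives no mortality rate and no sample-size argument based on mortality, so there is no figure to reproduce. The check is of the data route, followed by an illustration of size.

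**Step 1: can a death outside hospital reach the data?**

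| Possible route | What the protocol says | Does it record such a death? |
|---|---|---|
| TOHDW (6.7.2.5, 6.8.4, 6.9) | Captures data for hospital encounters | Not as described; death-date linkage is neither stated nor ruled out |
| 3-month visit (6.9) | Questionnaire and service review, in person | No; a patient who has died does not attend, and no follow-up of non-attenders is described |
| Outreach calls at 3 and 12 months (2.0) | For frail patients with the most severe disease | Not listed as a study data source in 6.8 |
| Electronic record and pathway documents (6.8.1) | Patient-related and some feasibility data | Mortality is assigned to the warehouse instead (6.8.4) |

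No registry link and no data from other hospitals are mentioned anywhere.

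**Step 2: illustrative size for mortality.** Inputs:
- N = 50, from 6.6.1: "We aim to recruit 50 unique patients over an 18-month period to use the care pathway".
- True 6-month mortality m = 10% to 20%: assumed.
- Share of deaths outside hospital and not captured, s = 30% to 60%: assumed.

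Missed deaths = N × m × s. Observed rate = m × (1 − s), if every patient without a recorded death were treated as alive.

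| m | True deaths | s | Missed deaths | Observed rate |
|---|---|---|---|---|
| 10% | 50 × 0.10 = 5 | 30% | 5 × 0.30 = 1.5 | 0.10 × 0.70 = 7% |
| 10% | 5 | 60% | 5 × 0.60 = 3 | 0.10 × 0.40 = 4% |
| 20% | 50 × 0.20 = 10 | 30% | 10 × 0.30 = 3 | 0.20 × 0.70 = 14% |
| 20% | 10 | 60% | 10 × 0.60 = 6 | 0.20 × 0.40 = 8% |

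A wider assumed range for s of 25% to 75% gives observed rates of 7.5% down to 2.5% when m = 10%, and 15% down to 5% when m = 20%.

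For scale, the exact 95% interval for 10 deaths in 50 is 10.0% to 33.7%. Most of the shift is no larger than sampling error in a study of this size, although the 8% case falls below that interval. Unlike sampling error, the shift always goes the same way.

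**Step 3: readmission.** Deaths at home or in hospice do not hide a readmission; only an admission to another hospital could. Taking the Project Summary's 20% (0.20 × 50 = 10 patients) and assuming 10% to 30% of readmissions occur elsewhere and are not captured, 10 × 0.90 = 9 down to 10 × 0.70 = 7 would be seen, that is 18% down to 14%. The 20% is itself cited to the same warehouse, so it may already carry the same limitation.

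**The case against.** The strongest reply is that the loss is inferred, not stated. The protocol does not say that TOHDW holds only this hospital's encounters or that it lacks dates of death, and the Data Specification Form is a natural place to settle both. This stands. A reader might infer that deaths outside hospital are certainly missed; the document supports only that they have no stated route into the data.

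Second, mortality may be meant as in-hospital mortality. It is listed beside initial length of stay, ICU admission and cost, and on that reading the source is suitable. The wording allows this, but the 6-month window is applied to all health service outcomes, so the outcome would still need its label.

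Third, a reader might infer that the pathway will appear to lower mortality because of where patients die. That needs a comparison. This is a single cohort with no comparator and no success threshold for mortality or readmission. Nor does the protocol state that patients without an encounter count as alive; the observed rates above assume it.

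Fourth, hospice, long-term care and palliative care at home appear together only in the terminally ill row. The severely and very severely frail row speaks of assisted living and advance care planning. How many of the 50 would fall in the terminally ill row is unknown, so extending the point to all of the sickest patients goes too far.

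Finally, a reader might extend the problem to readmission over 6 months. Six months is the collection window; the outcome is 30-day readmission, and only admissions elsewhere bear on it.

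These points narrow the claim but do not remove it. The protocol itself fixed the source and the window, and as described the two do not match for deaths outside hospital.

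**Conclusion.** The point holds in limited form. Post-discharge mortality may be undercounted because its only named source is described as an encounter database, while the pathway directs terminally ill patients to settings where a death need not produce an encounter. The size cannot be known from the protocol. The figure of 1.5 to 6 missed deaths among 50 patients rests on assumed mortality of 10-20% and an assumed 30-60% of deaths outside hospital; only the 50 is documented. If TOHDW carries linked dates of death, the number is zero and the protocol only needs to say so. For 30-day readmission there is a problem only if admissions to other hospitals are not captured.

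The affected items are descriptive secondary metrics. The primary feasibility outcome, recruitment and pathway completion, is untouched. The point is worth correcting because these figures feed the planning named in objective (c).

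**What to change.** 1. Check whether the Data Specification Form provides death-date linkage and data from other hospitals. If it does, say so in 6.7.2.5 and 6.9, and state the mortality window.
2. If it does not, relabel the TOHDW outcomes in both sections as *death during a captured hospital encounter* and *30-day readmission captured in TOHDW*.
3. At the planned 3-month contact, record vital status and any admission elsewhere. For patients who do not attend, add a chart check or a call. Fields on the visit form alone would miss those who have died, and a chart check confined to this hospital's records may share the gap, so a call is needed where the chart is silent.
4. Report 3-month mortality with the number of patients of unknown status shown, and do not count patients without an encounter as alive.

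The cost is some relabelling, two fields on a form and brief follow-up of non-attenders among 50 patients. Section 6.4 tells patients to expect two questionnaires, so it should be checked that the consent covers a call. The downside is that mortality is reported to 3 months rather than 6 unless linkage is available.
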